7.2 Recording and Grading

7.2.1 *Recording*

All observed or volunteered adverse events, regardless of treatment group, severity, suspected causal relationship, expectedness, or seriousness will be documented.

Radium-223

MSKCC

PCCTC LOI: c13-124

IRB#: 14-098 A (5)

A clinically significant change in a physical examination finding or an abnormal test result (i.e., laboratory, x-ray, EKG) should be recorded as an AE, if it:

- Is associated with accompanying symptoms
- Requires additional diagnostic testing or medical or surgical intervention
- Leads to a change in study dosing or discontinuation from the study
- Requires additional concomitant drug treatment or other therapy, or
- Is considered clinically significant by the investigator

An abnormal test result that is subsequently determined to be in error does not require recording as an adverse event, even if it originally met one or more of the above criteria.

7.2.2 *Grading severity*

All adverse events will be graded based on NCI CTCAE version 4.0

7.2.3 *Attributing causality*

After grading for severity, the investigator must evaluate all clinical AEs and abnormal laboratory values for possible causal relationship to the investigational agent. Causality attribution will be decided using the criteria outlined in Table 6.

Table 6 Relationship of Adverse Event to Study Drug

Relationship	Description
Unrelated	AE is clearly not related to Ra-223
Unlikely	AE is doubtfully related to Ra-223
Possible	AE may be related to Ra-223
Probable	AE is likely related to Ra-223
Definite	AE is clearly related to Ra-223

Abnormal laboratory values of clinical significance that were present at baseline and did not change in severity or frequency during experimental therapy or intervention and those that can obviously be attributed to underlying disease will be recorded as unrelated and will not be considered when evaluating the maximum tolerated dose (MTD).

7.3 Reporting Adverse Events

7.3.1 *Reporting serious adverse events*

All SAEs, events determined to be medically significant by the treating Investigator, and unknown reactions or unexpected events should be reported lead site/sponsor and PCCTC within 24 hours of knowledge of the event using the contact information below. The initial report should include the following information at a minimum:

- Protocol # and title

- study identification number, sex, age at time of event
- Date the event occurred
- Description of the SAE
- Causal relationship to the study drug

The PCCTC SAE Report Form (Appendix B) will be used for reporting each SAE and should be submitted to the PCCTC within 3 calendar days of learning of the event. Severity, causality, action taken, concomitant medications, outcome, etc should be reported to the PCCTC as soon as possible.

Follow-up of adverse events should continue until the event and any sequela resolve or stabilize at a level acceptable to the investigator.

The PCCTC will facilitate all SAE reporting to the MSKCC IRB/PB within 5 calendar days of PCCTC awareness or identification of the event.

SAE contact information for the PCCTC, lead site/sponsor is listed below:

Lead Site Study PI
[name]
Memorial Sloan Kettering Cancer Center
Genitourinary Oncology Service
[name]
[name]
[contact]

PCCTC:
Prostate Cancer Clinical Trials Consortium
[contact]
Email: [contact]

7.3.2 *Reporting SAEs to Bayer Pharmaceuticals, the drug supplier*

All serious adverse events should be reported to Bayer within 24 hours of learning of the event. If any subject dies during the trial or within 30 days of the end-of-treatment visit, the investigator will inform Bayer and record the cause of death in detail (using the SAE Form) within 24 hours of learning of the event.

Requirements for Reporting of Serious Adverse Events:

All SAEs must be reported to Bayer within 24 hours of the Principal Investigator's awareness and must include the following minimum information:

1. The name and contact information of the reporter
2. The name of the study drug(s)
3. A description of the reported SAE

4. A patient identified by one or more of the following:
 - a. Patient initials
 - b. Patient number
 - c. Knowledge that a patient who experienced the adverse event exists
 - d. Age
 - e. Sex

7.4 Safety Reports

PCCTC will distribute outside safety reports to the participating sites immediately upon receipt. Participating sites are responsible for submitting safety reports to their local IRB/PB as per their local IRB guidelines. All local IRB approvals/acknowledgments of safety reports must be sent to PCCTC upon receipt.

8. CRITERIA FOR OUTCOME ASSESSMENT/THERAPEUTIC RESPONSE

8.1 Primary endpoint

The primary endpoint of the study is a 30% decline in the BPI worst pain item from baseline to week 8, with a confirmed reduction at week 12 without an escalation of the subject's pain regimen from Step 1 to Step 2 or Step 2 to Step 3 of the WHO analgesic ladder.

The baseline BPI worst pain score average will be based on the worst pain scores completed by the patient in the 7 consecutive pretreatment days. A minimum of 4 days of pain scores must be completed by the patient in the 7 day window in order to calculate the average worst pain score.

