3.3 Exclusion Criteria

Patients that meet any of the criteria listed below will not be eligible for study entry:

- Prior exposure to Radium-223
- Received an investigational therapy within the 4 weeks prior to registration, or is scheduled to receive one during the treatment period
- Received a new anti-cancer agent within 4 weeks prior to registration
- Received external beam radiotherapy within 4 weeks prior to registration
- Received systemic therapy with radionuclides (e.g. strontium-89, samarium-153, rhenium-186 or rhenium-188) for the treatment of bone metastases
- Treatment with cytotoxic chemotherapy within 4 weeks prior to registration
- Symptomatic nodal disease, i.e. scrotal, penile or leg edema.
- Visceral metastases (including cerebral metastases) from CRPC (>2 lung and/or liver metastases [size $\geq 2\text{cm}$]; Lymphadenopathy exceeding 6 cm in short-axis diameter or any

Radium-223

MSKCC

size pelvic lymphadenopathy if it is thought to be a contributor to concurrent hydronephrosis), as assessed by CT, MRI or chest X-ray within the 8 weeks prior to registration

PCCTC LOI: c13-124

IRB#: 14-098 A (5)

- Concurrent chemotherapy. Patients may be on other non-chemotherapy anti-cancer treatments, per FDA labeling of Radium-223, provided that these are not changed during the primary pain assessment period
- Major surgery within 30 days prior to registration
- Imminent spinal cord compression based on clinical findings and/or magnetic resonance imaging (MRI). Treatment should be completed for spinal cord compression.
- Patients with a, “currently active,” second malignancy other than non-melanoma skin cancers or non-invasive bladder cancers or other in-situ or non-invasive malignancies. Patients who have completed therapy for a prior malignancy and are free of disease for ≥ 3 years are eligible.
- Any other serious illness or medical condition, such as but not limited to:
 - Any infection \geq National Cancer Institute Common Terminology Criteria for Adverse Events (NCI-CTCAE) version 4.0 Grade 2
 - Cardiac failure New York Heart Association (NYHA) III or IV
 - Crohn’s disease or ulcerative colitis
 - Bone marrow dysplasia
 - Fecal incontinence
- Any other condition which, in the opinion of the Investigator, would make the subject unsuitable for trial participation

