5.7 Concomitant Medications

Because of the potential for drug-drug interaction, the concurrent use of all other drugs, over-the-counter medications, or alternative therapies taken within 2 weeks prior to the start of the study must be documented on the case report form (CRF).

Patients receiving bisphosphonates or denosumab (RANK-L inhibitor) may continue on these agents as standard practice throughout the study.

Patients who enter the trial receiving prednisone or steroids must continue on the same dose they were receiving at the time of baseline assessment.

Permitted

- Pain Regimen Modification Guidelines:
 - An attempt to optimize a pain regimen should be made prior to subject enrollment. The investigator will optimize the subject's pain regimen under advisement/guidance of the 2.2014 NCCN Adult Cancer Pain guidelines. Opioid rotation, use of adjuvants, institution of a sustained release medication to minimize frequent prn dosing will be utilized depending on the severity of pain, degree of opioid tolerance and side effects under advisement/guidance of the NCCN guidelines. Use and optimization of short acting opioids followed, if needed, by adding an extended-release or long-acting formulation described in the protocol reflect NCCN guidelines. The patient will usually be allowed rescue doses of short-acting opioids of 10% to 20% of 24-h oral dose (mg) as needed as per the NCCN guidelines.
 - At the time of enrolment, the subjects pain regimen will be graded according to the WHO analgesia ladder:

Radium-223

MSKCC

PCCTC LOI: c13-124

IRB#: 14-098 A (5)

- Step 1- non-opioid analgesics
- Step 2- weak opioid (tramadol, codeine, hydrocodone)
- Step 3- strong opioid analgesic (morphine, oxycodone, fentanyl, oxymorphone, levorphanol, and methadone).
- NSAIDs, steroids and other adjuvant non-opioid analgesics can be included at each step of the analgesics ladder.
- Treatment with non-conventional therapies (e.g., herbs [with the exception of St. John's Wort], acupuncture) and vitamin/mineral supplements is acceptable provided that, in the opinion of the investigator, such treatment will not interfere with the trial endpoints.
- Subjects may receive standard of care for any underlying illness.

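### The analgesic clause of the primary endpoint counts only changes of WHO step, so pain relief from more opioid within a step, above all at Step 3, can be scored as a radium-223 response

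*Combined protocol and SAP*

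**What the plan says.** The responder rule appears in the synopsis and in Sections 8.1, 10.1.1 and 10.2.1. Each full statement disqualifies a pain response only if there is escalation of the "pain regimen from Step 1 to Step 2 or Step 2 to Step 3 of the WHO analgesic ladder". None contains a dose or opioid-equivalent term.

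Section 5.7 sets the grading: "At the time of enrolment, the subjects pain regimen will be graded according to the WHO analgesia ladder". The highest grade is "Step 3- strong opioid analgesic (morphine, oxycodone, fentanyl, oxymorphone, levorphanol, and methadone". The same section includes:

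- on preparation: "An attempt to optimize a pain regimen should be made prior to subject enrollment"
- on rescue: "The patient will usually be allowed rescue doses of short-acting opioids of 10% to 20% of 24-h oral dose (mg) as needed"
- on adjuvants: "NSAIDs, steroids and other adjuvant non-opioid analgesics can be included at each step of the analgesics ladder"
- on steroids: "Patients who enter the trial receiving prednisone or steroids must continue on the same dose they were receiving at the time of baseline assessment"

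No matching constancy rule is stated for opioids. Sections 3.2 and 3.3 do not exclude patients who are already at Step 3. Section 3.3 permits other non-chemotherapy anti-cancer treatment, "provided that these are not changed during the primary pain assessment period".

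Intake is recorded in a daily analgesic diary during the run-in and the pain assessment periods (Section 5, schedule footnote h; Section 5.4). Section 10.1.2 plans to convert analgesic use to equivalents and compare it before and after treatment, as a secondary analysis. The secondary analgesic endpoint in Section 8.2 is again by WHO step.

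**The concern.** The clause is there so that relief from stronger analgesia is not credited to radium-223. For a patient at Step 3 it cannot do that, because neither listed move is open to him. For a patient at Step 1 or 2 it works only if the step changes, so a higher dose of the same class passes.

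Entry at Step 3 is plausible. Patients must have an average worst pain of at least 3 although the regimen is to be optimised before entry.

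With no control arm, nothing else in the primary analysis separates relief due to analgesic from relief due to the drug. The background text suggests that the two can mix. In the earlier dose-response study (Section 1.2.1), mean diary pain is reported to have fallen by 12 mm in the group classed as pain progression, and that group was allowed to increase analgesics. This does not measure the effect here, but it makes the question reasonable.

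What is at stake is how each response counted towards 6/27 and 17/63 can be interpreted.

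**Working it through.** **1. Which routes the clause catches.**

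| Change after enrolment | Disqualified by the clause? |
|---|---|
| Step 1 to Step 2 | Yes, listed |
| Step 2 to Step 3 | Yes, listed |
| Step 1 directly to Step 3 | Not literally listed; probably intended |
| Higher dose within Step 1 or Step 2 | No |
| Higher dose or more rescue opioid within Step 3 | No; no higher step exists |

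**2. Whether anything else closes the gap.**

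- Optimisation before entry makes later increases less likely but does not bar them.
- Confirmation at week 12 does not help if the higher dose continues.
- The constancy rules cover steroids in patients who enter on them, and anti-cancer treatment, but not opioids.
- Review of responses by the response committee (Section 9.2.1) applies the rule and does not change it.
- The opiate-equivalent comparison (Section 10.1.2) would show rising use, but it is not tied to responder status.

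**3. The plan's own operating characteristics.** Inputs from Section 10.1.1: 27 patients in stage 1, stop at 5 or fewer responses; 36 more patients; success at 17 or more of 63. For a scored response rate p,

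P(effective) = sum over x = 6 to 27 of Pr[Bin(27, p) = x] × Pr[Bin(36, p) ≥ 17 − x].

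This gives 0.0999 at p = 0.20 and 0.9019 at p = 0.35. The stated 0.10 and 0.90 are reproduced.

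**4. Sensitivity to responses that come only from added analgesic.** Let s be the share of patients in whom such a rise would escape the clause, and d the extra probability of response that it causes among them. Both are assumptions; the documents give neither. If the true rate is 0.20 and is meant to be free of such relief, the scored rate is 0.20 + s × d.

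| Example s, d | Scored rate | Extra responders in 63 | P(effective) |
|---|---|---|---|
| d = 0 | 0.20 | 0 | 0.100 |
| 20%, 5 points | 0.21 | 63 × 0.01 = 0.6 | 0.140 |
| 40%, 5 points | 0.22 | 63 × 0.02 = 1.3 | 0.187 |
| 40%, 10 points | 0.24 | 63 × 0.04 = 2.5 | 0.304 |

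Solving P(effective) = 0.20 gives a scored rate of 0.2224, which is 63 × 0.0224 = 1.4 extra responders on average.

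**5. Whether any increase could serve as the re-scoring trigger.** Rescue opioid is taken as needed, so use varies by chance. If use is stable, the run-in, week 8 and week 12 means are exchangeable, and the run-in mean is the highest only about one time in three. Simulating stable Poisson rescue use of 0.3 to 4 doses a day over 7-day windows (assumption), 57% to 64% of patients exceed their run-in mean in at least one later window with no true increase. If half of responders were such users and 63% of them were re-scored, a true rate of 0.35 would appear as 0.35 × (1 − 0.5 × 0.63) = 0.24, and the chance of reaching the success rule would fall from 0.90 to 0.30. A trigger on any increase would therefore say little, and a margin is needed.

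**The case against.** The strongest reply is that a step-based rule is a deliberate and workable choice and that the bias is unquantified. For added opioid to create a false response, it must produce a 30% fall at week 8 that is confirmed at week 12, in a patient whose regimen was to be optimised beforehand. That stands, and it is why the primary rule should be kept. It does not show that such responses cannot occur.

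The second reply is that the data are already collected. Section 10.1.2 does not restrict the equivalents comparison to group level, so a cross-tabulation by response needs little more than an added sentence. That also stands. It makes the fix cheap but does not make it unnecessary, since nothing in the plan commits to it.

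A reader might go further and infer three things that the documents do not support:

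- **That the type I error is really 0.19 or 0.30.** Those figures rest on assumed s and d. The stated 0.10 is correct for the endpoint as scored, and the documents do not say whether 0.20 already allows for relief of this kind.
- **That the primary endpoint must be rewritten around dose.** The gap can be examined in a sensitivity analysis.
- **That a direct Step 1 to Step 3 move is meant to pass.** It is missing from the literal list, but such a move is an escalation by any ordinary reading.

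**Conclusion.** The point holds on the text. At Step 3 the clause has no force, and within Steps 1 and 2 it ignores dose. Existing safeguards reduce the problem, but none makes rising opioid use count against response or links it to individual responders.

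The size is unknown and may be zero. The calculation shows only that the decision rule is sensitive: under the assumption that 0.20 excludes such relief, an average of 1.4 extra responders in 63 doubles the chance of a false positive declaration. This is a cheap improvement to the analysis plan. It does not show that the design is invalid.

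**What to change.** Change scoring and reporting only. Pain treatment and the primary rule stay as they are. In Section 10.1.1 add:

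> Responders will be tabulated by WHO step at enrolment and by change in mean daily opioid equivalents from the run-in window to the week 8 and week 12 windows. Sensitivity analysis: responders whose mean daily opioid equivalents in the week 8 or week 12 window exceed the run-in mean by more than a margin the sponsor fixes before responders are counted are re-scored as non-responders, and the re-scored count is reported beside the primary count. Responders with too few diary days to judge are shown as a separate category, with the count given both with and without them.

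The sponsor also needs to say how many diary days are enough, because no minimum is set for weeks 8 and 12. The 4-of-7 rule for baseline pain scores in Section 8.1 is an obvious candidate. Wherever the responder rule is stated, clarify that a direct Step 1 to Step 3 move counts as an escalation.

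**Cost.** A little more analysis, using a diary and a conversion that are already planned. The sensitivity count will be conservative, because a true responder whose opioid use rose for another reason is re-scored. It does not detect increases in non-opioid analgesics. The 0.10 and 0.90 of the primary test are unchanged.

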8.2 Secondary endpoints

- Bone-ALP response will be described as:
 - Percentage of change from baseline to 12 weeks (or earlier for those who discontinue study therapy)
 - Maximum change (rise or fall) in bone-ALP during the treatment period reported for each patient as a waterfall plot
- Changes in total-ALP will be defined as for bone-ALP above
- PSA decline will be reported on all patients. Using PCWG2 guidelines ¹, the percentage of change in PSA from baseline to 12 weeks, as well as the maximum decline in PSA will be reported for each patient using a waterfall plot.
- Progression, for those patients showing an initial decline in PSA from baseline, is defined as an increase in PSA that is $\geq 25\%$ and ≥ 2 ng/mL above the nadir, and which is confirmed by a second value 3 or more weeks later (i.e., a confirmed rising trend).
- Progression, for those patients with no decline in PSA from baseline, is defined as an increase in PSA that is $\geq 25\%$ and ≥ 2 ng/mL after 12 weeks. Note: PSA progression as such will not lead to study discontinuation
- Time to First Radiographic or Clinical Progression (TTFROCP) based on RECIST version 1.1 and Prostate Cancer Working Group 2 (PCWG2) definitions
- Changes in other bone markers:
 - Serum C-telopeptide (sCTX-1)
 - N-terminal propeptide of procollagen type 1 (PINP)
- Radiographic response through the RECIST criteria 1.1 will also be determined using FDG PET/CT to assess for treatment effect in bone.
- Time to pain progression, defined as time until a ≥ 2 point increase in pain compared to baseline confirmed at least 4 weeks later.
- Change in analgesic use assessed by the WHO analgesic ladder
- Changes in measure of tiredness measured by the worst fatigue item (item #3) from the Brief Fatigue Inventory.
- Measures of pain interference specifically evaluating its affect on general activity and sleep as assessed on BPI
- Evaluate the short and long term toxicity to treatment

8.3 Therapeutic Response

Response and progression will be evaluated in this study using a combination of the revised

Radium-223

MSKCC

PCCTC LOI: c13-124

IRB#: 14-098 A (5)

international criteria proposed by the Response Evaluation Criteria in Solid Tumors (RECIST 1.1) committee and the guidelines for prostate cancer endpoints developed by the Prostate Cancer Clinical Trials Working Group (PCWG2).

Trial objectives are defined based on controlling, relieving, or eliminating disease manifestations that are present when treatment is initiated. Traditional measures of response reflect when a treatment is working and measures of progression indicate when a drug should be stopped. Because assessing response in bone (the most common site of prostate cancer spread) is uncertain and the clinical significance of PSA changes in response to therapy is not a reliable predictor of response, measures of response have been expanded in consortium trials to include measures of progression.

Patients will need to be reevaluated for response every 12 weeks \pm 1 week during protocol therapy according to the guidelines below.

8.3.1 *PSA*

Perform PSA testing at a minimum of 1-week intervals with the threshold PSA level at 2.0 ng/mL To report PSA-based outcomes, PCWG2 recommends that the percent of change in PSA from baseline to 12 weeks (or earlier for those who discontinue therapy) and the maximum decline in PSA that occurs at any point after treatment be reported for each patient using a waterfall plot. Because declines in serum PSA, if they occur, may not do so for several weeks, PSA measurements obtained during the first 12 weeks should not be used as the sole criterion for clinical decision making.

8.3.2 *Measurable disease*

According to RECIST 1.1, measurable disease is defined as at least 1 lesion \geq 10 mm in its longest diameter as measured with conventional techniques (i.e., CT or MRI). To be considered pathologically enlarged and measurable, a lymph node must be \geq 15 mm in short axis when assessed by CT scan. All tumor measurements will be taken using a ruler or calipers and recorded in millimeters (or decimal fractions of centimeters).

8.3.3 *Nonmeasurable disease*

Following RECIST 1.1, all other lesions (or sites of disease) will be considered nonmeasurable disease. This includes small lesions (longest diameter $<$ 10 mm or pathological lymph nodes with \geq 10 to $<$ 15mm short axis) and any of the following:

- Bone lesions
- Ascites
- Pleural or pericardial effusion
- Lymphangitis cutis or pulmonis
- Abdominal masses that are not confirmed and followed by imaging techniques
- Cystic lesions
- Lesions occurring within a previously irradiated area unless they are documented as new lesions since the completion of radiation therapy

- Leptomeningeal disease

Note: If only a single, asymptomatic bone lesion is present at baseline, and will be irradiated, the metastatic nature of this lesion must be confirmed by x-ray, CT, or MRI.

8.3.4 *Target (nodal and visceral) lesions*

Following RECIST 1.1, progression in a nodal or visceral site (i.e., liver and lung) is sufficient to document disease progression. The presence or absence of nodal and visceral disease before and after treatment should be recorded separately.

All measurable lesions (up to a maximum of 2 lesions per organ and 5 lesions in total) will be identified as target lesions to be measured and recorded at baseline. The target lesions should be representative of all involved organs. Target lesions will be selected on the basis of size (i.e., the largest area) and suitability for accurate, repeated measurements (either by imaging techniques or clinically). A sum of the diameters (longest for non-nodal lesions, short axis for nodal lesions) for all target lesions will be calculated and reported as the baseline sum diameters. The baseline sum of diameters will be used as a reference by which to characterize the objective tumor response.

Pathological nodes which are defined as measurable and may be identified as target lesions must meet the criterion of a short axis of $\geq 15\text{mm}$ by CT scan.

8.3.5 *Bone lesions*

On bone scan, progression of bone metastases is defined as the appearance of 2 or more new bone lesions.

- If 2 or more new bone lesions are observed on the first reassessment scan only, a confirmatory scan performed at least 6 weeks later needs to show 2 or more additional new lesions (for a total of 4 or more new lesions since the baseline assessment) for progression to be documented.

- If 2 or more new bone lesions are observed on scans obtained after the first reassessment, a confirmatory scan performed at least 6 weeks later needs to show the persistence of or an increase in the number of bone lesions compared to the prior scan.

The date of progression is always the date of the scan in which the change was first observed.

8.3.6 *Nontarget lesions*

All other lesions (or sites of disease) will be identified as nontarget lesions and recorded at baseline. Nontarget lesions will include measurable lesions that exceed the maximum number per organ (2) or total of all involved organs (5), as well as nonmeasurable lesions. The presence or absence of these lesions will be recorded on the CRF and should be evaluated at the same assessment time points as all target lesions.

8.3.7 *New lesions*

The appearance of up to 5 new measurable lesions should be recorded. Each new lesion should be reassessed using the same imaging modality at each time point. If measurable, the diameter of each new lesion should be recorded in the CRF and the sum diameters of new and old lesions should be calculated.

Note: The appearance of a new lesion does not by itself satisfy the criteria for confirmed progressive disease. Rather, the tumor burden imposed by the new lesions must be evaluated within the context of the total tumor burden (i.e., preexisting plus new lesions). Confirming progression in target lesions, non-target (i.e., other than bone) lesions, and bone lesions requires 2 assessment time points. The first must occur at Week 12 (or later) and the second occurring at least 6 weeks after the first. Progression declared at the first time point remains unconfirmed unless assessments at the second time point demonstrate continuing or worsening progression, as described in Section 9.4.

